MCV	Mean corpuscular volume
mg	Milligram
MI	Multiple imputation
Migraine Attack	An episode of any qualified migraine headache. The following rules will be used to distinguish an attack of long duration from two attacks, or to distinguish between attacks and relapses: 
 a) A migraine attack that is interrupted by sleep, or temporarily remits, and then recurs within 48 hours (ie, ≤ 48 hours between the start of the migraine attack to the time of the recurrence) will be considered as one attack and not two. b) An attack treated successfully with medication but with relapse within 48 hours (ie, ≤ 48 hours between the start of the migraine attack to the time of the recurrence) will be considered as one attack.
Migraine Day	Any calendar day in which the subject experiences a qualified migraine headache (onset, continuation, or recurrence of the migraine headache). A qualified migraine headache is defined as a migraine with or without aura, lasting for ≥ 30 minutes, and meeting at least one of the following criteria (a and/or b): 
 a) ≥ 2 of the following pain features: 
 • Unilateral • Throbbing • Moderate to severe • Exacerbated with exercise/physical activity b) ≥ 1 of the following associated symptoms: 
 • Nausea and/or vomiting • Photophobia and phonophobia 
If the subject took a migraine-specific medication (ie, triptan or ergotamine) during aura or to treat headache on a calendar day, then it will be counted as a migraine day regardless of the duration and pain features/associated symptoms.

Migraine-specific medications	Triptans and ergotamine-derivatives
mL	Milliliter
MNAR	Missing not at random
Monthly Headache Days	Number of headache days in any 28-consecutive day interval relative to study day 1
Monthly Migraine Days	Number of migraine days in any 28-consecutive day interval relative to study day 1
ng	Nanogram
NOAEL	No observed adverse effect level
NSAID	Nonsteroidal anti-inflammatory drug
OLTP	Open-label treatment phase

Abbreviation or Term	Definition/Explanation
PC	Product complaint
PCR	Polymerase chain reaction
PD	Pharmacodynamic
PE	Physical examination
PET	Positron emission tomography
PFS	Pre-filled syringe
pg	Picogram
PGt	Pharmacogenetics
PK	Pharmacokinetic
pM	Picomolar

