10.1.1.5 Definitions of Terms Included in Endpoints

Migraine Day: Any calendar day in which the subject experiences a qualified migraine headache (onset, continuation, or recurrence of the migraine headache). A qualified migraine headache is defined as a migraine with or without aura, lasting for ≥ 30 minutes, and meeting at least one of the following criteria (a and/or b):

- a) ≥ 2 of the following pain features:
 - Unilateral
 - Throbbing
 - Moderate to severe
 - Exacerbated with exercise/physical activity
- b) ≥ 1 of the following associated symptoms:
 - Nausea and/or vomiting
 - Photophobia and phonophobia

If the subject took a migraine-specific medication (ie, triptan or ergotamine) during aura or to treat headache on a calendar day, then it will be counted as a migraine day regardless of the duration and pain features/associated symptoms.

Headache Day: Any calendar day in which the subject experiences a qualified headache (initial onset, continuation or recurrence of the headache). A qualified headache is defined as:

- a qualified migraine headache (including an aura-only event that is treated with acute migraine-specific medication), or
- a qualified non-migraine headache, which is a headache that lasts ≥ 30 minutes and is not a qualified migraine headache, or

- a headache of any duration for which acute headache treatment is administered.

Acute Headache Medication Treatment Day: Any calendar day during which the subject took an acute headache medication (migraine-specific or non-migraine-specific).

Acute Migraine-specific Medication Treatment Day: Any calendar day during which the subject took a migraine-specific medication (ie, triptan or ergotamine).

Monthly eDiary Data: Data collected by the eDiary in any 28-consecutive day interval relative to study day 1 when **at least** 14 days of eDiary data are collected within that 28-consecutive day interval. **Monthly frequency measurements will be prorated to 28-day equivalents.**

Migraine Attack: An episode of any qualified migraine headache. The following rules will be used to distinguish an attack of long duration from two attacks, or to distinguish between attacks and relapses:

- a) A migraine attack that is interrupted by sleep, or temporarily remits, and then recurs within 48 hours (ie, ≤ 48 hours between the start of the migraine attack to the time of the recurrence) will be considered as one attack and not two.

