6.1 Definition of Terms Included in Study Endpoints

6.1.1 Efficacy Endpoints

The baseline period for efficacy analysis is defined as the period between week -4 visit (when eDiary device is set up or eDiary device assignment date) and the day prior to study day 1 (study day 1 is not included).

Migraine Day

Any calendar day in which the subject experiences a qualified migraine headache (onset, continuation or recurrence of the migraine headache). A qualified migraine headache is defined as a migraine with or without aura, lasting for ≥ 30 minutes, and meeting at least one of the following criteria (a and/or b):

a) ≥ 2 of the following pain features:

- Unilateral
- Throbbing
- Moderate to severe
- Exacerbated with exercise/physical activity

b) ≥ 1 of the following associated symptoms:

- Nausea and/or vomiting
- Photophobia and phonophobia

If the subject took a migraine-specific medication (ie, triptan or ergotamine) during aura or to treat headache on a calendar day, then it will be counted as a migraine day regardless of the duration and pain features/associated symptoms.

Monthly Migraine Days

Number of migraine days between each monthly IP dose. Monthly migraine days at baseline is the number of migraine days in the baseline period. Days without eDiary data in each monthly interval are handled by proration according to [Section 9.3](#).

Headache Day

Any calendar day in which the subject experiences a qualified migraine or non-migraine headache (initial onset, continuation or recurrence of the headache). A qualified headache is defined as:

- a qualified migraine headache (including an aura-only event that is treated with acute migraine-specific medication), or
- a qualified non-migraine headache, which is a headache that lasts ≥ 30 minutes and is not a qualified migraine headache, or
- a headache of any duration for which acute headache treatment is administered.

Monthly Headache Days

Number of headache days between each monthly IP dose. Monthly headache days at baseline is the number of headache days in baseline period. Days without eDiary data in each monthly interval are handled by proration according to [Section 9.3](#).

Migraine Attack

An episode of any qualified migraine headache or migraine specific medication intakes for aura only. The following rules will be used to distinguish an attack of long duration from two attacks, or to distinguish between attacks and relapses:

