6.4 Study Time Intervals

Monthly Interval for Efficacy Endpoints

Monthly efficacy measurements will be calculated based on the subject's monthly IP dosing schedule defined below using eDiary data collected from beginning of the baseline phase (week -4 visit) up to week 76 (end of eDiary use). Any eDiary data occurring after EOS date will not be included in the analysis.

Study Phase	Assessment Timepoint	Start Date	End Date
Baseline Phase	Baseline	LogPad assignment date (Week -4 study visit)	Day prior to study day 1
Double-blind Treatment Phase	Week 4	
• Study Day 1	
• Week 4 dose date-1• Study day 28 if Week 4 dose is not received (either missed or IP discontinued prior to Week 4)
	Week 8	
• Week 4 dose date• Study day 29 if Week 4 dose is not received (either missed or IP discontinued prior to Week 4)	
• Week 8 dose date-1• Study day 56 if Week 8 dose is not received (either missed or IP discontinued prior to Week 8)
	Week 12	
• Week 8 dose date	
• Week 12 IP dose date-1• Study day 84 if Week 12

		
• Study day 57 if Week 8 dose is not received (either missed or IP discontinued prior to Week 8)	dose is not received (either missed or IP discontinued prior to Week 12)
	Week 16	
• Week 12 dose date• Study day 85 if Week 12 dose is not received (either missed or IP discontinued prior to Week 12)	
• Week 16 dose date-1• Study day 112 if Week 16 dose is not received (either missed or IP discontinued prior to Week 16)
	Week 20	
• Week 16 dose date• Study day 113 if Week 16 dose is not received (either missed or IP discontinued prior to Week 16)	
• Week 20 IP dose date-1• Study day 140 if Week 20 dose is not received (either missed or IP discontinued prior to Week 20)
	Week 24	
• Week 20 dose date• Study day 141 if Week 20 dose is not received (either missed or IP discontinued prior to Week 20)	
• Week 24 IP dose date-1• Study day 168 if Week 24 dose is not received (either missed or IP discontinued prior to Week 24)

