10.7.1 Exposure-Response Analysis

Exposure-Response (E-R) analysis will be performed. Please refer to the E-R SSAP for additional details.

11. Changes from Protocol-specified Analyses

N/A

12. Literature Citations / References

- Fitzmaurice GM, Laird NM and Ware JH. (2004). Applied Longitudinal Analysis. New York: John Wiley and Sons.
- Breslow, N. E. and Clayton, D. G. (1993), Approximate Inference in Generalized Linear Mixed Models, *Journal of the American Statistical Association*, 88, 9–25.
- Wolfinger, R. and O'Connell, M. (1993), Generalized Linear Mixed Models: A Pseudo Likelihood Approach, *Journal of Statistical Computation and Simulation*, 4, 233–243.
- Rubin, D. B. (1987), Multiple Imputation for Nonresponse in Surveys, New York: John Wiley & Sons, Inc.
- Heinze, G. and Schemper, M. (2002), A Solution to the Problem of Separation in Logistic Regression, *Statistics in Medicine*, 2002; 21:2409–2419.
- Quade, D. (1966), Rank analysis of covariance, University of North Carolina, Institute of Statistics Mimeo Series. No. 483
- Fairclough DL1, Cella DF. Functional Assessment of Cancer Therapy (FACT-G): non-response to individual questions. *Qual Life Res*. 1996 Jun;5(3):321-9.

13. Prioritization of Analyses

The tables, listings and figures for Flash Memo of primary analysis at week 24 will be prioritized.

14. Data not Covered by This Plan

There are no plans to specifically analyze or summarize the following data points.

- ECG interval data
- PK
- CCI [REDACTED]
- CCI [REDACTED]

15. Appendices

Appendix A. Technical Detail and Supplemental Information Regarding Statistical Procedures and Programs

A1 Generalized Linear Mixed Model

Generalized mixed effects repeated measure model fits data with correlations or nonconstant variability and where the response is not necessarily normally distributed, which is also known as generalized linear mixed models (GLMM). The correlations can arise from repeated observation of the same sampling units, shared random effects in an experimental design, spatial (temporal) proximity, multivariate observations, and so on.

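### Monthly migraine days use fixed 28-day intervals in the protocol but dose-to-dose intervals in the SAP: an undeclared difference that can cost a late-dosed subject one month of the primary endpoint

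*SAP*

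**What the plan says.** The protocol glossary defines monthly migraine days as "Number of migraine days in any 28-consecutive day interval relative to study day 1". Protocol 10.1.1.5 defines monthly eDiary data in the same way ("Data collected by the eDiary in any 28-consecutive day interval relative to study day 1"), requires at least 14 diary days inside that 28-day interval, and prorates frequencies to 28 days.

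The SAP does something else. Section 6.1.1 defines the quantity as "Number of migraine days between each monthly IP dose". Section 6.4 states: "Monthly efficacy measurements will be calculated based on the subject's monthly IP dosing schedule defined below". In the table that follows, each month runs from one actual dose date to the day before the next. The study-day limits (85–112, 113–140 and 141–168 for months 4, 5 and 6) apply only when a dose is missed or treatment has stopped, for example "Study day 112 if Week 16 dose is not received". A dose that is late but given moves the boundary.

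SAP 9.3 sets a month with fewer than 14 diary days to missing and prorates the rest to 28 days. Under the heading "11. Changes from Protocol-specified Analyses" the SAP enters only N/A.

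Protocol Section 7 allows ±3 days around visit targets counted from day 1. Protocol 6.2.1.2 foresees delayed doses and names no maximum delay.

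**The concern.** Months 4, 5 and 6 make up the primary endpoint, and the two documents cut them differently. Under the SAP the length and position of each month depend on when doses are given after randomisation. Under the protocol they do not.

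The SAP's fallback is also uneven. A subject who misses the Week 16 dose gets a regular month 5 (days 113–140). A subject who receives that dose late can have month 5 cut below the 14-day minimum with no diary day missing. That month is then absent from the primary mixed model, carried forward from the lengthened month 4 under LOCF, and counted as non-response in by-visit responder analyses (SAP 9.3.3). SAP 7.5 can also exclude the subject from the Per Protocol Set for lacking an observed monthly value at Week 16, 20 or 24.

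The amendment does not explain the mismatch. The SAP was written to Protocol 1.0, and the change log for Protocol 10.1.1.5 shows the 28-day, study-day-1 interval both before and after the change.

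**Working it through.** **Inputs.** Dose targets are day 85 (Week 12), 113 (Week 16), 141 (Week 20) and 169 (Week 24), from the SAP 6.4 visit table. The visit window is ±3 days (Protocol Section 7). Interval rules come from SAP 6.4 and the 14-day rule from SAP 9.3. For power, SAP 3.2 gives effects of 1.12 and 1.30, SD 2.8, 131 per arm and two-sided 0.05. The diary is taken as complete throughout.

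**1. The plan's own figure.** Power = Φ(δ/SE − 1.96), with SE = 2.8 × √(2/131) = 0.346.
- 70 mg: 1.12/0.346 − 1.96 = 1.28, power 89.9%.
- 140 mg: 1.30/0.346 − 1.96 = 1.80, power 96.4%.

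The noncentral t gives 89.7% and 96.3%. The stated 90% and 96% reproduce, and the interval rule does not enter the calculation.

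**2. Dosing inside the window.** The SAP length of a month is the next dose day minus the current dose day. Target gaps are 28 days, so lengths run from 28 − 6 = 22 to 28 + 6 = 34 days. All are at least 14, so no month is lost. The calendar days still differ from the protocol's whenever a dose is off target.

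**3. How late a dose must be to lose the next month.** Let a dose be *k* days late and the next dose be *e* days off target. The month between them has 28 + *e* − *k* days and is missing when this is below 14, that is, when *k* ≥ 15 + *e*.
- Next dose 3 days early (*e* = −3): *k* ≥ 12.
- Next dose on time: *k* ≥ 15. The same holds if it is missed, because the month then ends at the study-day limit.
- Next dose 3 days late (*e* = +3): *k* ≥ 18.

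**4. Cases.**

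| Dose days (Wk 12, 16, 20, 24) | SAP month 4 | SAP month 5 | SAP month 6 |
|---|---|---|---|
| 85, 113, 141, 169 | 28 days | 28 days | 28 days |
| 85, 120, 141, 169 | 35 days | 21 days | 28 days |
| 85, 127, 140, 169 | 85–126, 42 days | 127–139, 13 days, missing | 140–168, 29 days |
| 85, 113, 155, 168 | 28 days | 113–154, 42 days | 155–167, 13 days, missing |

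On the protocol's grid every one of these months has 28 diary days. In the second row the share of diary days needed changes in both directions: 14/35 = 40% for month 4 and 14/21 = 67% for month 5, against 14/28 = 50% on the grid.

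**5. A bound on power.** The documents give no rate of late doses, so the rates here are assumptions. If 1%, 2%, 5% or 10% of subjects were lost entirely (n = 131 × (1 − f) per arm), power would be 89.6/96.2%, 89.3/96.1%, 88.4/95.6% or 86.7/94.6%. This overstates the loss, because one late dose removes one month and the mixed model keeps the others.

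**The case against.** The other side has several fair points.

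- **Dose-to-dose months are a legitimate choice.** Protocol 10.5.1 leaves statistical detail to the SAP. That supports the choice, but it does not make the two definitions agree or excuse the N/A in SAP Section 11.
- **The SAP 6.4 visit table may limit the damage.** It maps days 100–127 to Week 16 and days 128–155 to Week 20. If those windows also label doses, a dose on day 128 is not a Week 16 dose, the study-day fallback applies, and nothing is lost. The SAP does not say that they do. Even on this reading the problem remains: day 127 lies inside the Week 16 window, day 140 lies within ±3 of the Week 20 target, and 13 days are left. A loss then needs a delay of 12 to 14 days followed by a next dose 1 to 3 days early.
- **Proration covers longer months.** This stands. A 42-day month does not inflate the count; what changes is which calendar days enter it. Baseline already varies from 28 to 35 days.
- **Fixed intervals also contain delayed-dose time.** This stands. With Week 12 on day 85 and Week 16 on day 127, the protocol's month 5 includes days 113–126, all 28 or more days after the last dose. Including such time is not a fault peculiar to the SAP.
- **The grid is not perfectly regular.** If month 6 must stop before open-label dosing, a first open-label dose on day 166 leaves 141–165, which is 25 days.

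A reader might infer that a late dose can wipe out months 4 to 6 together, or that the rule biases the comparison or weakens the trial materially. The documents support neither. One late dose removes at most one month and lengthens the one before it. No direction of bias can be shown, and even the exaggerated 5% loss moves power for 70 mg only from 89.9% to 88.4%.

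**Conclusion.** The conflict is real and undeclared. The primary endpoint has two derivations, and they agree only when doses fall exactly on target. Within the visit window the effect is a shift of boundaries with prorated counts and no lost month. The loss of one month despite a complete diary is confined to doses roughly 12 to 18 days late, or 12 to 14 days if the visit windows are taken to label doses.

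This rests on the SAP 6.4 table as written, on a next dose within ±3 days of target or missed, and on a complete diary. The number of such subjects is not given and is probably small. The point should be settled because it leaves two documented definitions of the primary endpoint open until one is chosen. It does not put the sample size in doubt.

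**What to change.** Before unblinding, state one definition identically in both documents. Either route works:

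1. **Study-day grid.** In SAP 6.1.1 and 6.4 derive months 1 to 6 as study days 1–28, 29–56, 57–84, 85–112, 113–140 and 141–168 for every subject, with month 6 ending no later than the day before the first open-label dose. These are the limits the SAP already uses for missed doses. Report dose-to-dose months as a sensitivity analysis.
2. **Dose-to-dose months.** Keep them, declare the change in SAP Section 11 and amend the protocol definition. Extend the study-day fallback to late doses as well as missed ones, so that a complete diary cannot yield a missing month. Say whether the SAP 6.4 visit windows label doses. Report the fixed 28-day grid as a sensitivity analysis.

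Neither route touches dosing or visit conduct. The cost is SAP wording and one extra derivation, plus a protocol wording change under the second route.

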6.1.2 Safety Endpoints

Serious Adverse Event (SAE)

SAEs determined by the flag indicating if the adverse event is serious on the Adverse Events eCRF page will include those that occur after signing of the informed consent and up to and including end of study.

Treatment-Emergent Adverse Event

Adverse Events (AEs) recorded on the Adverse Events eCRF page that occurs on or after first dose of investigational product as determined by the flag indicating if the adverse event started prior to the first dose on the Adverse Events eCRF and up to and including 112 days after the end of investigational product (16 weeks after the last dose of IP) or end of study, whichever comes earlier.

Serious Treatment-Emergent Adverse Event

A serious treatment-emergent adverse event is an SAE considered to be treatment-emergent.

Treatment-Related Adverse Event

A treatment-related AE is defined as a treatment-emergent adverse event that is considered by investigators to have reasonable possibility that it may have been caused by IP as determined by the flag indicating if the event is caused by investigational product on the Adverse Events eCRF page.

Serious Treatment-Related Adverse Event

A serious treatment-related adverse event is an SAE considered to be treatment-related.

Columbia-Suicide Severity Rating Scale (C-SSRS)

The C-SSRS is a clinician rating of suicidal behavior and ideation. Two versions depending on the type of visits will be used in this study: Screening and Since Last Visit. The C-SSRS consists of a maximum of 20 items to evaluate suicidal behavior and suicidal ideation.

Beck Depression Inventory (BDI)-II

The Beck Depression Inventory (BDI)-II is a 21-item questionnaire that assesses severity of depression. Each item is scored from 0 to 3. The total score is categorized into 4 severity grades: minimal depression (0-13), mild depression (14-19), moderate depression (20-28), and severe depression (29-63).

6.2 Study Dates

Informed Consent Date

The date on which subject signs the informed consent form.

eDiary Device Assignment Date

The date on which an eDiary device is assigned to a subject for the first time after completion of initial screening at week -4 visit.

Randomization (Enrollment) Date in DBTP

Randomization (Enrollment) Date in DBTP is the date on which a subject is assigned to one of the treatments through Interactive Voice Response System (IVRS) in DBTP.

First IP Dose Date

First IP Dose Date is the date on which a subject is administered the first dose of investigational product following randomization, which may be the same day or after the randomization date. For subjects who are randomized but not dosed with double-blind IP after randomization, First IP Dose Date is considered missing.

First OLTP IP Dose Date

First OLTP IP Dose Date is the date on which a subject is administered the first dose of investigational product in the open-label treatment phase following completion of DBTP.

Last IP Dose Date

Last IP Dose Date for each subject is defined as the latest date IP is administered.

End of IP Admin Date

End of IP Admin for each subject is defined as the date the decision was made to end IP as recorded on the End of IP eCRF page.

Subject-level End of Study (EOS) Date

End of study (EOS) date for each subject is defined as the last date on which the subject participated in the study. The date will be recorded on the End of Study eCRF page.

Primary Completion Date

The Primary Completion Date is the date of the End of Double-Blind Treatment Phase page for the last subject who completes DBTP.

Study Completion Date

The Study Completion Date is the EOS date of the last subject in the study.

6.3 Study Points of Reference

Baseline Assessment

Baseline assessment is defined as the last non-missing measurement for the endpoint of interest taken before the first dose of investigational product. In cases where baseline measurements are taken on the same day as IP, it will be assumed that these measurements are taken prior to IP being administered. For subjects who are randomized but not dosed after the randomization, the baseline of the study is defined as the last non-missing measurement prior to or on the date of randomization.

For C-SSRS, if subject completes C-SSRS form on Day 1 then all individual items from Day 1 visit will be used as baseline. If subject does not complete C-SSRS form on Day 1 then all individual items from Week -4 visit will be used as baseline.

Baseline assessment of data collected from eDiary will be summarized as monthly measurements using data collected during baseline period. See [Section 6.1.1](#) for detail.

Study Day 1

Study Day 1 is defined as the first IP dose date. For subjects who are randomized but not dosed after randomization, the Study Day 1 is defined as the date of randomization.

Study Day

Study Day is defined as the number of days from Study Day 1.

Before Study Day 1:

Study Day = (Date of Interest – Date of Study Day 1)

On or after Study Day 1:

Study Day = (Date of Interest – Date of Study Day 1) + 1

Therefore the day prior to Study Day 1 is -1.

